4.1.1.6 MG0011 data

Based on the protocol specifications, for participants who entered DV0013 from the MG0011 parent study, only ongoing medications are rolled over to the DV0013 clinical database. Thus, for such participants, the DV0013 study outputs of medical history, past and prior medications, history of *Neisseria meningitis* vaccinations and history of medical procedures will be populated with data already collected in the parent study. A raw data snapshot of MG0011 will be considered close to the DV0013 data base lock date in order to obtain the related data. The date of the MG0011 snapshot will be footnoted in the related DV0013. The MG0011 records that will be kept within DV0013 for each participant will be restricted to data with start date prior to Visit 1.

4.1.2 Definition of baseline values

The Baseline value is defined as the last non-missing measurement prior to the first self-injection at Day 1 (Visit 1)

If a scheduled Baseline assessment is taken on the same day as the first administration of study medication, then the assessment will be assumed to have been performed prior to study medication.

Change from Baseline (CFB) is defined as the value minus baseline value.

Percent Change from Baseline is defined as $100 \times (\text{Change from Baseline} / \text{Baseline})$.

4.1.3 Mapping of assessments performed at Early Discontinuation Visit

If a participant prematurely discontinues study intervention at any time prior to Visit 8, the participant should return to clinic for a stand-alone Early Withdrawal Visit. C-SSRS is the only assessment to be performed at that visit that will be mapped to the next scheduled visit (which is Visit 8).

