**Table 1-1: Schedule of study assessments**

Period	Screening Period	Treatment Period								EW b (In-clinic)	SFU Visit c (Phone call)
		Day 1 (In-clinic)	Day 2 (Phone call) a	Day 4 (Phone call) a	Day 6 (Phone call) a	Day 8 (Phone call) a	Day 10 (Phone call) a	Day 12 (Phone call) a	Day 14 (In-clinic)		
Name	Screening (In-clinic)										
Visit #	1		2	3	4	5	6	7	8		9
Day	1		2	4	6	8	10	12	14		(Final dose +7±3 days)

d Participants may rescreen twice (total of 3 screenings).

e The full physical exam will include examination of the following systems: eyes, hair, and skin; respiratory; cardiovascular; and gastrointestinal systems. The Investigator should examine the injection site at each scheduled visit for injection site reactions (eg, bruising, pain, swelling, pruritis, and hematoma). Any abnormalities should be reported as AEs. Height and weight will also be measured and recorded at Visit 1. A full physical exam will be performed at Visit 1 and Visit 8. Any findings will be reported as AEs as appropriate. Any clinically significant changes since the physical examination at Visit 1 will be recorded as AEs.

f Vital signs (sitting systolic and diastolic blood pressure, pulse rate, and temperature) are to be measured prior to blood sampling and prior to dosing, where applicable.

g For women of childbearing potential, pregnancy testing will consist of urine pregnancy tests at Visits 1 and 8 only. Pregnancy test results must be negative prior to administering IMP. Positive urinary test will be exclusionary. Participant may rescreen at a later time if pregnancy not confirmed subsequently with a serum test.

h When recording the final dose taken prior to enrolling in DV0013, the time of self-administration should also be recorded. Participants should continue on the same weight-based dose that they were self-administering in MG0011 or commercial ZLP dose they were on prior to enrolling in DV0013.

i A single question will be asked at Visit 8 postdose, assessing the study participant's preference for administration method.

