## 7.2 Participant discontinuation/withdrawal from the study

Participants are free to withdraw from the study at any time, without prejudice to their continued care.

A participant may withdraw from the study at any time at his/her own request or may be withdrawn at any time at the discretion of the Investigator for safety, behavioral, compliance, or administrative reasons.

If the participant withdraws consent for disclosure of future information, the Sponsor may retain and continue to use any data collected before such a withdrawal of consent.

If a participant withdraws from the study, he/she may request destruction of any samples taken and not tested, and the Investigator must document this in the site study records.

See the SoA (Section 1.3) for data to be collected at the time of study discontinuation and follow up and for any further evaluations that need to be completed.

Participants should be withdrawn from the study if any of the following events occur:

1. Participant develops an illness that would interfere with his/her continued participation.
2. Participant is noncompliant with the study procedures or medications in the opinion of the Investigator.
3. Participant withdraws his/her consent.
4. There is confirmation of a pregnancy during the study, as evidenced by a positive pregnancy test. If the study participant was enrolled from MG0011, the study participant should roll back into MG0011, and MG0011 protocol procedures should be followed. Participants recruited from commercial supply should go back to using commercial supply and follow the guidance in the regional-approved product label.
5. The Sponsor or a regulatory agency requests withdrawal of the participant.
6. The Investigator is of the opinion that the participant's continued participation in the study is not in the best interest of the participant.
7. Participant experiences a severe or serious injection site reaction (eg, bleeding, bruising, or pain) or a SAE that would, in the opinion of the Investigator, preclude the participant's further participation in the study.

Study participants who withdraw from DV0013, ie, study participants who have a medical condition or personal preference that precludes further self-administration, must perform a SFU telephone call or equivalent 7 days ( $\pm$  3 days) after their final DV0013 dosing visit.

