4.1.1 Analysis time points

Summaries by study visits will be performed at the nominal visits and no mapping to analysis visits windows will be performed, except for early termination visit as specified in Section 4.1.3. Unscheduled visits (if any) will only be listed and will not be remapped. An individual participant listing indicating the actual visit dates will be created in SS.

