4.1.1.2 Missing data

Missing data for any of the study endpoints or any other data will not be imputed (except for missing date and times, see Section 4.1.1.4); observed cases will only be used in the summary.

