4.5.3 Tolerability - Injection Site Reactions and Medication Errors

Injection Site Reactions

An AE reported in the eCRF with a start date/time on or following to the first self-administration of ZLP AI through the final self-injection and until the safety follow up which is coded into MedDRA High Level Terms of “Administration site reactions NEC” or “Injection site reactions” will be evaluated as Injection Site Reaction (ISR). ISRs will be summarized in SS overall, by intensity and by seriousness. Summaries will be based on the number and percentage of participants who experienced at least one ISR event by MedDRA SOC, HLT and PT followed by the number or ISR events.

A separate assessment of tolerability at injection site (as part of physical examination and as defined in the study protocol) is performed during the on- site visits assessing pain, burning, erythema, itching, swelling and bruising based on a Likert type scale of 0 to 3. Greater grade indicates more severe injection site reaction. For each of the assessments a shift table will be created to show the shift of injection site reaction grading from Visit 1 to Visit 8.

ISR and tolerability data will be listed in SS.

Medication Errors

An adverse reaction is a response to a medicinal product which is noxious and unintended (Directive 2001/83/EC, Article 1 (11)). An adverse event which is reported as a consequence of a medication error is considered as an adverse reaction.

Participants with medication errors associated with adverse reactions will be identified via the eCRF- Adverse Event form as reported by the investigator. The number and proportion of participants experiencing such AEs during the Intervention Period will be summarized by MedDRA SOC, HLT and PT in SS. A by-participant listing in SS will also be created listing all the AEs associated with medications errors reported in the study.

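### The injection-site tolerability shift tables leave out participants who withdraw before Visit 8, including those withdrawn for a severe reaction, so they can understate severe grades

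*SAP*

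**What the plan says.** SAP 4.1.3 covers participants who stop before Visit 8 and return for a stand-alone EW visit. Its rule is that "C-SSRS is the only assessment to be performed at that visit that will be mapped to the next scheduled visit (which is Visit 8". SAP 4.1.1 closes other routes: summaries use nominal visits, and "no mapping to analysis visits windows will be performed, except for early termination visit as specified in Section 4.1.3".

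SAP 4.5.3 introduces "A separate assessment of tolerability at injection site (as part of physical examination and as defined in the study protocol", made at the on-site visits. Pain, burning, erythema, itching, swelling and bruising are each graded 0 to 3, and for each of them "a shift table will be created to show the shift of injection site reaction grading from Visit 1 to Visit 8". No EW column or last-visit rule is given. Under SAP 4.1.1.2 nothing is imputed and "observed cases will only be used in the summary". SAP 4.1 bases percentages in safety summaries on participants with data unless otherwise specified, displays that denominator, and prescribes a missing category only for demographics and baseline characteristics.

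Protocol Table 1-1 marks the physical examination at Day 1, Day 14 and the in-clinic EW visit. Its footnote e adds: "The Investigator should examine the injection site at each scheduled visit for injection site reactions". Protocol 7.2, criterion 7, gives this ground for withdrawal: "Participant experiences a severe or serious injection site reaction (eg, bleeding, bruising, or pain", qualified by the Investigator's opinion on whether the participant can continue.

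For the C-SSRS, by contrast, SAP 4.5.5.4 defines the last visit as Visit 8 or EW.

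**The concern.** A shift table is read as a before-and-after account of the treated group. Here the after column is limited to people who reached Visit 8, and one route out of the study before Visit 8 is a bad reaction at the injection site. Whether a participant appears can therefore depend on the variable being tabulated. A severe grade that leads to withdrawal cannot appear in the Visit 8 column.

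The objective that this display serves is the safety and tolerability of self-administration with the auto-injector. At stake is whether six small descriptive tables (one per sign or symptom) describe everyone who used the device or only those who used it to Day 14. The SAP gives no reason for carrying the C-SSRS from EW to Visit 8 while leaving the tolerability grade behind.

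**Working it through.** **Planned size.** The plan states at least 25 participants, 14 self-administrations each and about 350 in total: 25 × 14 = 350, which agrees. The documents give no expected withdrawal or ISR rate and no power figure, so what follows is an illustration on N = 25.

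**How the rules combine**
1. The grade is shown at Visit 1 and Visit 8 only (SAP 4.5.3).
2. An EW grade is not carried to Visit 8 (SAP 4.1.3), and no other mapping is allowed (SAP 4.1.1).
3. Missing Visit 8 grades are not imputed (SAP 4.1.1.2), and safety percentages use participants with data (SAP 4.1).
4. So a participant who withdraws before Visit 8 has no end-of-treatment entry, whatever was seen at EW.

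**Formula.** Let w participants withdraw before Visit 8, of whom k are grade 3 at EW, and let s of the remaining N − w be grade 3 at Visit 8.
- As written: s / (N − w).
- With EW grades included: (s + k) / N.

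The second is a weighted average of s / (N − w) and k / w. Including EW grades therefore raises the severe share only if severe grades are commoner at EW than at Visit 8.

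**Illustration.** Assume s = 0 and that every withdrawn participant is still grade 3 at EW (k = w). Intervals are exact 95% (Clopper-Pearson). They show how little 25 people can say; the SAP plans no interval for these tables.

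| Withdrawals (assumed) | As written | EW included |
|---|---|---|
| 0 | 0/25 (0 to 13.7%) | 0/25 (0 to 13.7%) |
| 1 | 0/24 (0 to 14.2%) | 1/25 = 4.0% (0.1 to 20.4%) |
| 2 | 0/23 (0 to 14.8%) | 2/25 = 8.0% (1.0 to 26.0%) |
| 3 | 0/22 (0 to 15.4%) | 3/25 = 12.0% (2.5 to 31.2%) |

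**When the assumptions fail**
- Reaction resolved by EW (k = 0, s = 0, w = 1): 0/24 against 0/25, so the severe share stays at zero.
- Withdrawal for another reason with a low grade, and one grade 3 at Visit 8 (k = 0, s = 1, w = 1): 1/24 = 4.2% as written against 1/25 = 4.0%, a slight move the other way.

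**How likely is at least one such withdrawal?** With an assumed per-participant chance p, it is 1 − (1 − p)^25: 22% at p = 1%, 40% at 2%, 72% at 5% and 93% at 10%.

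**The case against.** **Is the grade recorded at EW?** The documents do not settle this. Table 1-1 marks a physical examination there, and SAP 4.5.3 speaks of on-site visits. But footnote e names the full examination at Visits 1 and 8, and Protocol 9.4.2 says physical examination findings enter the eCRF only at Screening/Day 1. Read literally, that sentence would also remove the Visit 8 grade that the SAP tabulates, so it does not decide the matter. The 0 to 3 scale itself is absent from the protocol text, although the SAP refers to the protocol for it. This objection stands. A reader might infer that the EW data already exist and need only be mapped; the documents make that likely but do not establish it.

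**Is an EW grade comparable with a Visit 8 grade?** Visits 1 and 8 include a witnessed injection. Table 1-1 schedules none at EW, which may fall days after the last dose. The grade may describe a resolving reaction, so keeping it apart from Visit 8 is defensible. This also stands, and it favours identifying EW values over merging them silently.

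**Is the reaction lost?** A reader might infer that severe reactions vanish from the safety report. They do not. SAP 4.5.3 summarises ISR adverse events in the whole Safety Set by intensity and seriousness and lists the tolerability data, and SAP 4.5.2.3 tabulates TEAEs leading to permanent withdrawal. Nor is it a fault in itself if the AE tables and the shift tables differ: one counts events over the study, the other compares two time points.

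**Does withdrawal follow from a reaction?** Only in part. Criterion 7 involves the Investigator's judgement, and Protocol 7.1 says stopping study medication should not automatically remove someone from the study. Such a person may still attend Visit 8 and be counted. No document equates a severe or serious reaction under criterion 7 with grade 3 on the tolerability scale.

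None of this changes the rule: a participant who leaves before Visit 8 is absent from the end-of-treatment column.

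**Conclusion.** The point holds in a limited form. By stated rule, participants who withdraw before Visit 8 have no end-of-treatment entry in the tolerability shift tables. Because a severe or serious reaction is itself a ground for withdrawal, those tables can understate severe grades. With 25 participants, each withdrawal still at grade 3 at EW is worth about 4 percentage points, if nobody else has grade 3.

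A reader might go further and infer that the tables always err in the favourable direction. The documents do not support that: if the reaction has settled by EW the severe share is unchanged, and an unrelated withdrawal with a low grade can move it slightly the other way.

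The number of withdrawals, the EW grade and the absence of other grade 3 results are assumptions, not figures from the plan. With no early withdrawal the results are identical under either rule. The effect is confined to a descriptive display of a measure that is not a listed endpoint in its own right. Severity is minor and confidence moderate, mainly because recording of the grade at EW is unconfirmed.

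**What to change.** 1. Confirm first whether the eCRF records the 0 to 3 grade at the EW visit.
2. If it does, define the display in SAP 4.5.3 as a shift from Visit 1 to Visit 8/EW, with EW values identified by a footnote count or a separate row. Amend SAP 4.1.3 to match, so that the C-SSRS is no longer the sole exception.
3. In either case, add a missing column so that each table accounts for the whole Safety Set. SAP 4.1 permits this, since its observed-data denominator applies only where nothing else is specified. If the grade is not recorded at EW, this column, with the reason for withdrawal, is the operative part of the change.

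The cost is about one sentence in each of SAP 4.1.3 and 4.5.3, an update to the separate table specifications and a little programming. The downside is that an EW grade comes before Day 14 and away from a scheduled injection visit, so it may reflect a resolving reaction; identifying the EW values lets the reader allow for that.

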4.1.4 Derivation of study arms and combinations for analysis

Not applicable, as this is a single arm open label study.

4.1.5 Multicenter studies

Centers are located in North America and Europe; data from all sites will be pooled to display any summaries. Individual center results will not be summarized.

4.1.6 Center pooling strategy

Individual center results will not be displayed.

4.2 Primary [estimand(s)/endpoint(s)] analysis

This section contains a detailed description of the analysis of the primary, secondary and other outcome measures. All statistical analyses will be descriptive in nature. No inferential statistical analysis is planned to be performed.

All data to assess the primary outcome are collected on the study medication administration page of the eCRF as recorded at Visit 1 (Day 1) and at Visit 8 (Day 14) per each ZLP-AI.

4.2.1 Definition of endpoint(s)

The primary estimand is defined in [Table 1–1](#) based on the Treatment Policy definition, regardless of intercurrent events.

The primary variable is the Effective self-administrations of zilucoplan using the ZLP-AI as captured in the study eCRF based on the investigator's opinion.

The Effective self-administration is defined as:

- Complete dose delivery: completeness of the delivery as confirmed by the Investigator. The entire dose of IMP should be completely delivered (ie, the yellow plunger that can be seen through the device window should be completely depressed).

Thus, the investigator should answer the following eCRF question for each ZLP-AI used and returned throughout the Intervention Period:

“Did the study participant self-inject the complete dose Zilucoplan (confirmed by visual inspection of the device window by the investigator, showing that the yellow plunger is completely depressed)?”

4.2.2 Main analytical approach

The proportion (p) of effective self-administrations overall will be summarized based on the number of ZLP-AIs used and returned, within participants in the Safety Set (SS):

$$P = [\text{Number of all ZLP-AIs with complete dose delivery}] / [\text{Number of all ZLP-AIs used and returned}]$$

The denominator of the fraction should include all ZLP-AIs that were used (self-administered) during the Intervention Period and returned, as captured in the drug accountability log. Of note, since it is possible that complete dose delivery may be observed within malfunctioned ZLP-AIs the denominator should also include the malfunctioned auto injectors (if any).

The 95% CI of the proportion based on the Exact Binomial method will be reported as well.

Based on the above calculation no missing data are expected to be observed.

In order to provide further insight into the evaluation of the primary estimand, the following will also be summarized:

- Number of injections performed by (study participant, site personnel, caregiver).

- Number of injections dispensed

- Number of injections returned, used and malfunctioned

- Number of injections returned used and not malfunctioned

- Number of injections returned, unused

- Reason for Discrepancy between dispensed and returned injections (lost, stolen, missing, other).

A by participant individual data listing will be created reporting detailed information on the ZLP-AIs kits administered and returned in clinic.

4.2.3 Sensitivity analysis

As a sensitivity analysis on the primary estimand the following will be considered in the Safety Set.

$$p = [\text{Number of all ZLP-AIs with complete dose delivery}] / \text{Number of all ZLP-AIs that should have been used in the Intervention Period.}$$

The number of ZLP-AIs that should have been used in the Intervention Period for each participant will be calculated as follows: [Date of last ZLP-AIs self-administration – Date of first ZLP-AIs self-administration + 1].

The 95% CI of the proportion based on the Exact Binomial method will be reported as well.

4.2.4 Supplementary analysis

No supplementary analysis is planned for the present study.

4.3 Secondary [estimand(s)/endpoint(s)] analysis

The secondary estimand is defined in Table 1–1 based on the Treatment Policy definition, regardless of intercurrent events.

The primary variable is the Effective self-administrations of zilucoplan using the ZLP-AI as captured in the study eCRF based on the investigator's opinion at each site visit (Visit 1 and Visit 8).

The Effective self-administration is defined as:

- Complete dose delivery: completeness of the delivery as confirmed by the Investigator. The entire dose of IMP should be completely delivered (ie, the yellow plunger that can be seen through the device window should be completely depressed).

Thus, for the investigator should answer the following eCRF question for the ZLP-AI used at each site visit:

“Did the study participant self-inject the complete dose Zilucoplan (confirmed by visual inspection of the device window by the investigator, showing that the yellow plunger is completely depressed)?”

The proportion (p) of effective self-administrations will be summarized in the Safety Set separately for Visit 1 and Visit 8:

- $P_{v1} = [\text{Number of all ZLP-AIs with complete dose delivery at Visit 1}] / [\text{Number of all ZLP-AIs used}]$
- $P_{v8} = [\text{Number of all ZLP-AIs with complete dose delivery at Visit 8}] / [\text{Number of all ZLP-AIs used}]$

The denominator of the fractions should include all ZLP-AIs that were used (self-administered) at Visit 1 and at Visit 8 respectively, as captured in the drug accountability log. Of note, since it is possible that complete dose delivery may be observed within malfunctioned ZLP-AIs the denominator should also include the malfunctioned auto injectors (if any).

The corresponding exact binomial 95% Confidence Interval of the proportions will be provided.

Based on the above calculation no missing data is expected to be observed.

A by participant individual data listing will be created reporting the ZLP-AIs administered and returned in clinic.

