**Table 3-1: Objectives and estimands/endpoints**

Objectives	Estimands/endpoints
	
 
Complete dose delivery: completeness of the delivery as confirmed by the Investigator. The entire dose of IMP should be completely delivered (ie, the yellow plunger that can be seen through the device window should be completely depressed)
 
Intercurrent event handling: 
 
No intercurrent event is defined
 
 
 
Population level summary: 
 
Proportion of participants, along with the 95% CI
 
 
 

 
Evaluate the safety and tolerability of the ZLP-AI self-administrations
 
	
Secondary endpoint:
 
 
Occurrence of SAEs, TEAEs, ADEs (serious and nonserious) from Visit 1 up to the SFU Visit
 

Other objectives	

 
Evaluate the PK of the ZLP-AI for self-administration
 
	
Other PK endpoint:
 
 
Measurement of plasma concentrations for zilucoplan and main metabolites CCI [REDACTED]
 

 
Evaluate the safety and tolerability of the ZLP-AI self-administrations
 
	
Other safety endpoints:
 
 
Occurrence of ISRs
 
Occurrence of medication errors associated with adverse reaction
 

 
Evaluate the safety of the ZLP-AI
 
	
Other safety endpoint:
 
 
Occurrence of SADEs related to the use of the ZLP-AI that would preclude continued use of the ZLP-AI for self-administration (ie, SADEs and/or SADEs leading to withdrawal from the DV0013 study)
 

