#### 9.3.1 Primary estimand/primary endpoint analyses

The primary outcome variable is defined in [Table 3-1](#).

The proportion of effective self-administrations will be tabulated for the ZLP-AI combination product using the SS population. The 95% CIs based on the Exact Binomial method will be reported. As a sensitivity analysis, the primary endpoint will also be evaluated, where any missing self-administration will be considered as an administration failure. In addition, the proportion of effective self-administrations may be described by geographical region as well.

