### 9.3.2 Secondary estimand/secondary endpoint analyses

The secondary outcome variables are defined in [Table 3-1](#).

The secondary outcome variables will be analyzed using the SS in the same manner as the primary outcome variable (Section [9.3.1](#)).

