4.8 Changes to protocol-planned analyses

The following changes have been applied in the current SAP vs the study protocol dated 15 December 2023.

Table 4–1: Changes from the DV0013 protocol

Study Protocol	Study SAP update

Definition:
 
Enrolled Set: all participants who have signed an informed consent form.
	
Definition
 
Enrolled Set: all participants who have signed an informed consent and are eligible candidates for the study (screen failures excluded).

Screened Set (ScS) has not been defined in the study protocol
	
ScS has been defined in the SAP as all participants who have signed the informed consent form.

For the primary estimand, as sensitivity analysis, any missing data were to be imputed as administration failure.
	
Sensitivity analysis has been removed because based on the definition of the primary estimand, no missing values are expected.

Population level summary of the secondary estimand regarding the complete dose delivery at Visit 1 and at Visit 8 is based on the proportion of participants:
 
Proportion of participants, along with the 95% CI.
	
Population level summary of the secondary estimand regarding the complete dose delivery at Visit 1 and at Visit 8 is based on the proportion of used ZLP-AIs and returned (for Visit 8). Therefore, the population level summary of the estimand has been phrased as:
 
Complete dose delivery: completeness of the delivery as confirmed by the Investigator at Visit 1 and at Visit 8. The entire dose of IMP should be completely delivered (ie, the yellow plunger that can be seen through the device window should be completely depressed)

Table 4–1: Changes from the DV0013 protocol

Study Protocol	Study SAP update
Population level summary of the secondary estimand regarding the complete dose delivery at Visit 1 and at Visit 8 by region was not defined.	Population level summary of the secondary estimand regarding the complete dose delivery at Visit 1 and at Visit 8 will be also displayed by region.

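### The Visit 8 secondary proportion is conditional on still using the auto-injector, which fits poorly with its treatment-policy label, and no supportive analysis counts participants who stopped earlier

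*SAP*

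**What the plan says.** Protocol Table 3-1 gives the population-level summary for the Visit 1 and Visit 8 endpoints as "Proportion of participants, along with the 95% CI". Protocol 9.3.2 adds that the secondary variables "will be analyzed using the SS in the same manner as the primary outcome variable". The primary analysis in Protocol 9.3.1 includes a sensitivity analysis "where any missing self-administration will be considered as an administration failure". Protocol 9.6, however, names that sensitivity analysis only for the primary estimand, and Protocol 3.1 restricts the analysis to observed data.

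SAP 4.3 counts devices. Its denominator rule reads: "The denominator of the fractions should include all ZLP-AIs that were used (self-administered) at Visit 1 and at Visit 8 respectively". It continues: "Based on the above calculation no missing data is expected to be observed". It labels the secondary estimand as defined "based on the Treatment Policy definition, regardless of intercurrent events". SAP 4.1.1.2 says: "Missing data for any of the study endpoints or any other data will not be imputed", apart from dates and times. SAP Table 4-1 declares the change from participants to used devices. It gives no reason for the change and does not discuss early stoppers.

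**The concern.** Visit 8 falls on Day 14, after a period in which the participant receives no further training. It is the natural place to ask whether self-administration is still effective at the end of the treatment period. As planned, the proportion answers this only for those who are still injecting.

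The Safety Set requires at least one auto-injector dose, and the first is scheduled at Visit 1. The Visit 1 proportion therefore covers essentially the whole Safety Set, while the Visit 8 proportion may cover fewer people. A reader who compares the two could take a difference in who is counted for a difference in performance. No missing data are expected only because non-use has been placed outside the denominator.

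Device-related stopping is foreseeable. Protocol 7.2 includes severe or serious injection site reactions and personal preference that precludes further self-administration, and SAP 4.5.2.3 plans a row for device-related events leading to permanent withdrawal.

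**Working it through.** **The plan's own figure.** 25 participants × 14 daily self-administrations = 350, which matches the approximate total in Protocol 9.8 and SAP 5. There is no power or effect size to reproduce.

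**Inputs.** n = 25 (Protocol 9.8 and SAP 5, as a minimum). One self-administration per participant per day (Protocol 6.1). Exact binomial 95% CI (SAP 4.3). The number of early stoppers, d, is not given, so 0 to 5 is assumed.

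**Formulas.** Let x be the number of complete deliveries at Visit 8.
- Planned: x / (n − d).
- Safety Set, with no Visit 8 self-administration counted as not effective: x / n.
- Gap: x·d / [n(n − d)]. If every Visit 8 injection is complete, x = n − d and the gap is d/n, or 1/25 = 4.0 points per stopper.
- Exact limits: the 0.025 quantile of Beta(x, N − x + 1) and the 0.975 quantile of Beta(x + 1, N − x), where N is the denominator used. The upper limit is 100% when x = N.

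**Results with every Visit 8 injection complete**

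| Stoppers | Planned (used at Visit 8) | Safety Set, none = not effective | Gap (points) |
|---|---|---|---|
| 0 | 25/25 = 100% (86.3 to 100) | 25/25 = 100% (86.3 to 100) | 0 |
| 1 | 24/24 = 100% (85.8 to 100) | 24/25 = 96.0% (79.6 to 99.9) | 4.0 |
| 2 | 23/23 = 100% (85.2 to 100) | 23/25 = 92.0% (74.0 to 99.0) | 8.0 |
| 3 | 22/22 = 100% (84.6 to 100) | 22/25 = 88.0% (68.8 to 97.5) | 12.0 |
| 5 | 20/20 = 100% (83.2 to 100) | 20/25 = 80.0% (59.3 to 93.2) | 20.0 |

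**Direction.** The planned figure can never be below the Safety Set figure, but it need not exceed the truth. Take two stoppers and one failure among the 23 users. The planned figure is 22/23 = 95.7% and the Safety Set figure is 22/25 = 88.0%. If both stoppers would have delivered complete doses, the full-set value is 24/25 = 96.0%, slightly above the planned figure.

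**Does another planned proportion restore the stoppers?**
- SAP 4.2.3 is a sensitivity analysis of the primary only, and its denominator ends at each participant's last administration. With 23 completers and two who stop on Day 5, it is 23 × 14 + 2 × 5 = 332, not 350.
- Compliance (SAP 6.10) counts days only up to the last scheduled or early withdrawal visit.
- Only the C-SSRS is mapped from early withdrawal to Visit 8 (SAP 4.1.3).
- No supplementary analysis is planned (SAP 4.2.4).

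None of these gives a Visit 8 proportion on the full Safety Set.

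**The case against.** The strongest reply is that the endpoint is delivery of a dose. Someone who made no injection at Visit 8 is outside that target, so the planned figure is correct for what it measures. That stands, provided the SAP says so. It is at odds with the treatment-policy label.

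A reader might infer more than the documents support:

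- **That the estimate is certainly biased upward.** Bias needs stopping to be linked to poor delivery. Protocol 7.2 also lists reasons that need not involve the device, such as illness, pregnancy, withdrawn consent and a sponsor request.
- **That changing from participants to devices caused the problem.** With one device per participant per day, the two units coincide at a single visit. Under the observed-data rule in Protocol 3.1, early stoppers would have had no Visit 8 value in a participant-level analysis either.
- **That the protocol plainly requires missing-as-failure at Visit 8.** The cross-reference in Protocol 9.3.2 can be read that way, but 9.6 names only the primary.
- **That attrition is hidden.** SAP 6.2 tabulates discontinuation reasons and participants per visit, and the stoppers' returned devices still count in the primary.

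The disposition tables do not settle everything. They use the Enrolled Set, and SAP 4.1.1.5 defines completion of the Intervention Period by the Visit 8 visit having been performed. Protocol 7.1 lets a participant stop study medication and remain in the study, so someone could attend Visit 8 without injecting and count as a completer.

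**Conclusion.** The point holds in a limited form. The Visit 8 proportion is conditional on use at Visit 8 and may overstate success if stopping is device-related. Its label suggests otherwise, and no planned proportion shows how much the restriction matters. The size depends on a dropout count that the documents do not give: zero with no stoppers, and 4 points per stopper if 25 participants enter and every Visit 8 injection is complete. With one failure among users and two stoppers, the gap is 7.7 points.

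The study is descriptive and unpowered, with no hypothesis test, so no decision turns on this. It is a cheap improvement in clarity, not the repair of an invalid analysis.

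**What to change.** - Keep P_v8. Describe it in SAP 4.3 as conditional on a self-administration at Visit 8, or reword the treatment-policy statement.
- Add one supportive row: Safety Set participants with complete dose delivery at Visit 8, divided by all Safety Set participants, with no Visit 8 self-administration counted as not effective and an exact 95% CI.
- Footnote the number without a Visit 8 injection by reason, with a cross-reference to the disposition table in SAP 6.2.
- In the same edit, write the visit into the displayed denominators. They now read as all devices used, and only the following text limits them to the visit.

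The cost is one table row and a footnote. The downside is a less favourable supportive figure if anyone stops early, and one that also counts stops unrelated to the device as failures. It should be presented as a conservative bound beside P_v8, not as a replacement.
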